3.1 Confidence intervals and p values

All tests are two-sided and the nominal level of alpha will be 5%. P-values will not be adjusted for multiplicity.

3.2 Analysis populations

All analyses will be conducted on an intention-to-treat (ITT) basis. All randomized participants will contribute to the final study analyses and will be analysed in the group to which they were assigned regardless of protocol violations. The only exception would be where a participant withdraws consent for participation and use of their data.

3.3 Subgroup analysis

Sub-groups will be limited, are pre-specified and described below in Section 5.2.1.

4 Trial Population

4.1 Eligibility

Participants were recruited from hospital or satellite centres with the capacity to offer haemodiafiltration and standard high flux haemodialysis.

All adult patients with ESKD who meet the inclusion and no exclusion criteria were considered eligible for this study.

Participants were eligible for INCLUSION in the study if ALL the following criteria are met:

1. Incident or prevalent patients requiring maintenance haemodialysis therapy for ESKD
2. Aged 18 years or older
3. Suitable for either haemodiafiltration or standard dialysis in the view of the treating physician
4. Agreeable to randomisation

Patients were EXCLUDED from the study if, in the opinion or knowledge of the responsible clinician the following criterion is present:

1. Life expectancy less than 6 months
2. Definite plans to undergo renal transplantation, transfer to a non-study site, transfer to peritoneal dialysis or transfer to home haemodialysis within 12 months of entry to the study
3. Receiving haemodiafiltration
4. Unable or unwilling to complete neuropathy staging, including nerve conduction studies.

4.2 Recruitment

Flow of patients through the study will be displayed in a CONSORT flow diagram. We will report the number of screened patients who met study inclusion criteria, the number randomised into the study, and the number available for the primary analysis (Figure 1). The reasons for exclusion will be documented at each step in the diagram.

4.3 Participant Follow-up and Withdrawal

All participants were asked to participate in an intervention phase that lasted from randomisation until the earliest of:

- Completion of 48 months in the trial from randomisation, or
- In-centre/ satellite haemodialysis therapy was no longer required (eg patient receives a kidney transplant, transfers to peritoneal dialysis, transfers to home haemodialysis), or
- Transfer to a dialysis unit not able to offer both study interventions, or
- Withdrawal of consent by the participant, or
- Participant death.

Participants withdrawn from the randomised treatment for any reason (either by choice or on advice from their physician) will be followed-up according to the study follow-up schedule and analysed according to the intention-to-treat principle, providing they consent to such follow-up.

The level of withdrawal (to intervention and/or follow-up), timing and reasons for withdrawal will be recorded and presented by treatment group.

4.4 Baseline Characteristics

Description of the following baseline characteristics will be presented by treatment group. Discrete variables will be summarized by frequencies and percentages. Percentages will be calculated according to the number of patients for whom data are available. Where values are missing, the denominator (which will be less than the number of patients assigned to the treatment group) will be stated in either the body or a footnote in the corresponding summary table. In some instances, additional frequencies and percentage of patients in each category will be reported as indicated in the list below. Continuous variables will be summarized by use of standard measures of central tendency and dispersion using mean and standard deviation and/or median and quantile points at 0.25, 0.5 and 0.75 where appropriate. Free text entries for fields collecting both categorical and free text information (eg ethnicity) will be assessed and assigned to a category if appropriate. No testing will be performed for differences in baseline characteristics between treatment arms, as per CONSORT.

Demographics

- Sex
- Age
- Ethnicity (ethnicities constituting 10% or more of the study population will be listed)

Medical History

- Primary cause of Renal disease (Categorized as Diabetic Nephropathy, Hypertension/ Vascular Nephropathy, Glomerulonephritis, Polycystic Kidney Disease, Other)
- Co-morbidities:
 - Diabetes Mellitus – type 1, type 2, nil
 - Hypertension
 - Ischaemic heart disease (Angina, Acute MI, Previous Coronary Artery Bypass/ Percutaneous Transluminal Coronary Angioplasty)
 - Congestive Heart Failure (NYHA classification)
 - Cerebrovascular Disease (rapid or focal neurological deficit lasting > 24 hours)
 - Peripheral Vascular Disease (requiring or having required peripheral revascularisation of carotid or peripheral artery, or amputation related to peripheral vascular disease)
 - Parathyroidectomy surgery
 - Previous fracture (Pathological fracture, Stress fracture, Traumatic fracture)
 - Carpal tunnel surgery
 - Other surgery on nerves
 - Peripheral neuropathy
 - Ovarian disease or bilateral oophorectomy (women only)
 - Menopausal status (women only)
- Smoking status (Categorized as Current smoker, Former smoker or Non-smoker)
- Dialysis
 - Site: home, centre (hospital and satellite)
 - Dialysis vintage (from ANZDATA)
 - Dialysis in last week: number of hours/session, number of sessions/week, number of hours/week
 - Timing of dialysis: day/night/combination of both
 - Access: native AVF, synthetic graft, tunnelled catheter, non-tunnelled catheter, other
 - Mode of access: buttonhole cannulation, rope ladder cannulation, Dialysis catheter, other
 - Anticoagulation (heparin, enoxaparin, nil or other and dose)
 - Dialysate composition: Sodium, Potassium, Calcium, Glucose

- Dialysis parameters: blood flow rate, dialysate flow rate, membrane, machine brand and model, dialysate temperature
- Medications
 - Phosphate binders, number and dose

Physical Examination

- Pre-dialysis blood pressure, average of 3 if available
- Height, weight, dialysis ideal body weight, BMI (derived from height and ideal body weight)
- Waist circumference, Hip circumference, Waist:hip circumference (derived from waist and hip circumferences)

Laboratory Measures

- Haematology: Haemoglobin, Total white blood cell count, Platelet count
- Biochemistry: Sodium, Potassium, Chloride, Glucose, Bicarbonate, Creatinine, Calcium (using corrected calcium formula^a), Phosphate (pre-dialysis), Calcium phosphate product (derived from calcium and phosphate), Albumin, C-reactive protein, Parathyroid Hormone
- Pre dialysis and post dialysis Urea, Small molecular clearance reported as either Urea Reduction Ratio or Kt/V
- β_2 -microglobulin levels (pre and post dialysis)
- Total cholesterol, Triglycerides
- Ferritin, Transferrin saturation
- HbA1c (if diabetic)
- Troponin (if available)
- B natriuretic peptide (if available)

^aThe corrected calcium will be calculated according to the following formula:

corrected calcium (in mmol/l) = measured calcium (in mmol/l) + ((40-albumin (g/l))x0.02)

Quality of Life Scores

- EQ-5D
- KDQOL SF-1.3
- KDRL

Neuropathy assessment (Appendix 1)

- Modified Total Neuropathy Score and stratification
- Neuropathy symptom score and Neuropathy symptom score stage, derived from neuropathy symptom score

5 Analysis

5.1 Outcome Definitions

Primary Outcome

The primary end-point for this study is the difference in the mean change in modified total neuropathy score (TNS) from baseline between the two groups.

Mean changes from baseline will be analysed using a restricted maximum likelihood (REML)-based repeated measures approach (MRMM). Analyses will include the fixed, categorical effects of treatment, visit (unstructured), and treatment-by-visit interaction, as well as the continuous, fixed covariates of baseline score and baseline score-by-visit interaction. We will test a range of covariance structures (autoregressive(1), heterogeneous autoregressive(1), unstructured, compound symmetry structure) and select the structure with

the lowest AIC (best fit). The Kenward-Roger approximation will be used to estimate denominator degrees of freedom. Analyses will be implemented using SAS/Stat 14.2.

The primary comparison will be the average of the contrast between treatment groups across all time points in the study, with each observed time-point weighted equally.

Secondary Outcomes

These will follow the same plan approach for the primary outcome (MRMM), with different comparisons and distributions for the outcomes as appropriate.

1) Neuropathy outcomes. Analyses will include:

- a) Difference between groups in mean change from baseline in modified TNS at years 1, 2, 3, 4 with the same method as the primary analysis
- b) Difference between treatment groups in proportion of participants with modified TNS 0-8 (no or minor neuropathy) overall (time-points weighted equally) and at 1, 2, 3 and 4 years, using a generalised linear mixed model with a binomial distribution and a logit link.¹
- c) Difference between groups in mean change from baseline in NSS overall (as per main outcome), and at 1, 2, 3 and 4 years with the same method as the primary analysis.
- d) Difference between treatment groups in proportion of participants with no or asymptomatic neuropathy on NSS (NSS stage 0-1) overall, and at 1, 2, 3 and 4 years using a generalised linear mixed model with a binomial distribution and a logit link .
- e) Difference between treatment groups in change in sural nerve sensory amplitude (mV) from baseline overall, and at 1, 2, 3 and 4 years with the same method as the primary analysis.

1. The intent of secondary outcome 1b is to evaluate the proportion of people with asymptomatic disease in each group. To allow each assessment to be categorised as either asymptomatic or symptomatic, we have specified a definitive mathematical range for each category, 0-8 and 9-28 respectively. The 0-8 range represents the 'asymptomatic' range which we are more accurately describing here as 'no or minor neuropathy'.

To limit the number of comparisons and risk of Type I error we will only test for differences in binary outcomes where there has been a difference detected ($p < 0.05$) in the analysis of the continuous variable, i.e. analysis of 1b will only proceed if there is a difference in a time point in 1a, and 1d proceeds if we find a difference in 1c.

2) Safety outcomes. Analyses will include:

- a) Time to access failure, defined as thrombosis or fistula requiring revision
- b) Number of discrete episodes of access failure, defined as above.
- c) Episodes of septicaemia defined as blood culture positive septic episode without defined source.

d) Mortality

e) Cardiovascular events (composite of: cardiovascular death or any of the following requiring or occurring during a hospital admission: acute myocardial infarction, cerebrovascular event, percutaneous coronary or cerebrovascular revascularisation, or surgical coronary or cerebral revascularisation)

f) Surgery for carpal tunnel syndrome

g) Parathyroidectomy surgery

h) Fractures requiring or occurring during a hospital admission

3) Durability:

Durability is defined as adherence to the intervention at each time point

4) Ranked composite endpoint combining mortality and TNS

5) Follow-up of long term events.

a) Long-term survival at 24, 36 and 48 months following the conclusion of individual's intervention period

b) Durability of the intervention at 12, 24, 36 and 48 months following the conclusion of individual's intervention period

These events will be analysed during the post-intervention cohort observation period and will be subject to a later Statistical Analysis Plan.

Exploratory analyses:

1) By components of modified TNS: Mean change in score from baseline to end of study for:

a. Clinical symptoms (sensory and motor symptoms)

b. Physical examination (pin sensitivity, strength, tendon reflexes)

c. Nerve conduction study (sural and tibial amplitudes)

2) Quality of life measures were collected at baseline and during the follow-up period. The analysis of quality of life measures will be part of a later Statistical Analysis Plan.

3) Repeat primary and appropriate secondary analyses using original (not modified) Total Neuropathy Score.

Inter-rater reproducibility of TNS:

Neuropathy assessments were undertaken by qualified neurologists and neurophysiologists and supervised by [name], who performed the measurements in the vanguard phase of the trial. Assessors were blinded to participant treatment allocation. [name] duplicated neuropathy assessments for 5 patients to allow assessment of inter-rater reliability. Inter-rater reliability will be estimated using the Spearman's rank correlation coefficient with a 95% CI as was performed by Cornblath et al in the original description of TNS[10].

Neuropathy assessment

Neuropathy will be assessed in all participants using two validated scoring systems that incorporate clinical symptoms, examination findings and results of nerve conduction studies:

(1) Modified Total Neuropathy Score (TNS), a validated measure of peripheral nerve function[10]. (Appendix 1)

(2) Neuropathy Symptom Score (NSS) which, in conjunction with nerve conduction findings, will be used to calculate a neuropathy stage[8, 11]. (Appendix 1)

The neuropathy scores will be obtained at baseline, annually and, where possible, at anticipated transfer to another modality of renal replacement therapy (transplant, peritoneal dialysis or home haemodialysis) or transfer to a non-study centre that cannot offer both interventions, by treatment group.

Intervention: Dialysis Treatment

The adherence to the treatment allocation (haemodiafiltration versus standard high flux) at each time point will be reported and analysed.

Achieved dialysis parameters will be reported in each allocation group, including:

- Blood flow rates and dialysate flow rates
- Convection volumes (for participants randomized to haemodiafiltration)
- Pre-dialysis systolic and diastolic blood pressure
- Dialysis prescription: number of hours/session, number of sessions/week, number of hours/week
- Dialysis site: in-centre/ hospital or satellite
- Dialysis access: native AV fistula, synthetic graft, tunnelled catheter, non-tunnelled catheter, other
- Dialysate composition: Sodium, Potassium, Calcium, Glucose, addition of phosphate

Variables will be presented as percentages for each group at baseline and 1, 2, 3 and 4 years.

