2.3 Sample Size

Total Neuropathy Score was selected to measure the primary endpoint as it met the requirements for neuropathy assessment as articulated in the 2005 Consensus Statement[7]. However, at the time the study was designed, *there were no available results for Total Neuropathy Score assessments in dialysis patients*. Accordingly power calculations were made using information on Neuropathy Symptom Score grades and sural nerve conduction values that were available when the study was designed[3, 8, 9]. Using assumptions based on those studies FINESSE was calculated as having more than 90% power to detect a reduction in moderate to severe neuropathy from 80% in the control arm to 48% prevalence in the treatment arm (absolute difference of 32%) with a sample size of 120 (with $\alpha=0.05$), including an allowance for 20% combined drop-out and loss to follow-up

(n=96 in the final analysis). We also calculated that with 90% power (with $\alpha=0.05$) the study could detect an absolute difference of 2.6mcV in the mean response of sural nerve sensory amplitudes between the treatment groups (assuming a standard deviation of 3.9).

Since developing the original protocol, studies have been conducted that provide data on the Total Neuropathy Score from an external cohort of dialysis patients ([name], personal communication). In 49 dialysis patients, the mean TNS was 9.2 (SD: 7.8) with 42% (20/48) having a TNS score of 17-32 (moderate to severe neuropathy). Using these assumptions, FINESSE has 90% power to detect a mean difference of 5.2 in TNS between treatment arms at the end of the study and 80% power to detect a mean difference of 4.5.

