5.2 Analysis methods

Subgroup analyses

The following pre-specified subgroup analyses will be conducted:

1. Baseline TNS: 9-28 vs 0-8
2. Diabetic vs not diabetic
3. Gender: M/ F
4. Baseline access type: AVF vs other (including graft/ catheter)
5. Dialysis vintage at randomisation: <12 months v ≥12 months

The access type will be separated into AVF verses other as the clear majority of participants (78%) were using an AVF at baseline. Baseline blood flow rate was considered for subgroup analysis but discarded as there was little variation across the cohort (baseline blood flow rate

median 300, 5th percentile 300, 95th percentile 330). Sub-group analyses will be completed by including an interaction between each sub-group and the treatment variable.

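### The primary model is valid but omits diabetes; adding it before unblinding would gain modest precision if diabetes predicts TNS change beyond baseline TNS

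*SAP*

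**What the plan says.** Section 5.1 (Primary Outcome) specifies a REML repeated-measures model for change in modified TNS. Its terms are treatment, visit and treatment-by-visit, "as well as the continuous, fixed covariates of baseline score and baseline score-by-visit interaction". No other covariate is named. Secondary outcomes 1a, 1c and 1e use the same method.

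Section 2.2 stratifies the 1:1 randomisation on baseline TNS stratum only (0–8 or 9–28).

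Diabetes appears in two other places. Section 4.4 lists it among the baseline characteristics, as "Diabetes Mellitus – type 1, type 2, nil". Section 5.2 names "Diabetic vs not diabetic" as one of five pre-specified subgroups, each analysed through an interaction with treatment. Neither section provides an overall treatment estimate adjusted for diabetes, and no sensitivity analysis does so.

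The SAP states neither how common diabetes is in the cohort nor how strongly it predicts change in TNS.

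**The concern.** The TNS scores symptoms, signs and nerve amplitudes whatever their cause (Appendix 1), so neuropathy due to diabetes enters the endpoint alongside uraemic neuropathy. Baseline TNS carries the damage present at entry. It need not carry a different rate of worsening over four years, which is what a change-from-baseline outcome measures. Any such difference stays in the residual and widens the primary interval, although the variable that could remove it is already on the baseline list.

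There is also a matter of credibility. If the arms happen to differ in diabetes, readers will ask for an adjusted result. One specified after unblinding would be post hoc.

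**Working it through.** **1. The plan's own power figures.** Inputs from Sections 2.3 and 3.1: SD 7.8, "n=96 in the final analysis" (48 per arm), two-sided alpha 0.05. The SE of a difference in means is 7.8 × √(2/48) = 1.592.

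- The plan states "FINESSE has 90% power to detect a mean difference of 5.2 in TNS between treatment arms". Recomputed: power 90.4% (noncentral t 89.8%); detectable difference (1.960 + 1.282) × 1.592 = 5.16.
- The plan states "80% power to detect a mean difference of 4.5". Recomputed: power 80.7% (noncentral t 79.9%); detectable difference 4.46.

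Both figures reproduce as an unadjusted comparison of two means, so neither depends on adjustment for diabetes.

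**2. Precision from adding diabetes.** The inputs here are assumptions: prevalence p = 30–50%; residual SD of the averaged change, after baseline TNS, of 5–6; extra worsening d in diabetics at a given baseline TNS of 0–4 points. For scale, an SD of 7.8 with an assumed baseline-to-follow-up correlation of 0.7 leaves 7.8 × √(1 − 0.49) = 5.57.

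Formulas: R² = p(1−p)d²/SD²; SE factor = √(1−R²); equivalent gain in patients = 1/(1−R²) − 1. Low end: p = 0.3, SD 6. High end: p = 0.5, SD 5.

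| d (points) | R² low | R² high | SE reduction |
|---|---|---|---|
| 0 | 0 | 0 | 0 |
| 1 | 0.21 × 1/36 = 0.6% | 0.25 × 1/25 = 1.0% | 0.3–0.5% |
| 2 | 0.21 × 4/36 = 2.3% | 0.25 × 4/25 = 4.0% | 1.2–2.0% |
| 3 | 0.21 × 9/36 = 5.25% | 0.25 × 9/25 = 9.0% | 2.7–4.6% |
| 4 | 0.21 × 16/36 = 9.3% | 0.25 × 16/25 = 16.0% | 4.8–8.3% |

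At d = 3 the gain equals 1/0.9475 − 1 = 5.5% to 1/0.91 − 1 = 9.9% more patients. A test with 80% power has a standardised effect of 1.960 + 0.842 = 2.802. Dividing by √0.9475 or √0.91 gives 2.878 or 2.937, so power becomes Φ(0.918) = 82.1% to Φ(0.977) = 83.6%.

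The formula treats diabetes as unrelated to baseline TNS. If the two are associated, less of the variation in diabetes is left to explain the residual, and the gain is smaller for the same d.

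**3. Chance imbalance.** The SD of the between-arm difference in prevalence is √(2p(1−p)/n).

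| Per arm | SD, p = 30% | SD, p = 50% | Chance of a difference of 10 points or more |
|---|---|---|---|
| 60 | 8.4 points | 9.1 points | 23–27% |
| 48 | 9.4 points | 10.2 points | 28–33% |

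A 10-point difference shifts the contrast by 0.10 × d, that is 0.2–0.4 TNS points for d = 2–4. With SD 5–6 and 60 per arm the SE is 5 × √(2/60) = 0.91 to 6 × √(2/60) = 1.10, so the shift is below half an SE.

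**4. Comparison with the adjustment already planned.** From the unadjusted 5.16, baseline TNS with an assumed correlation of 0.5–0.7 lowers the difference detectable at 90% power to between 4.47 and 3.69. Diabetes explaining 2–15% of the variance would lower 5.16 to between 5.11 and 4.76. Under these assumptions the larger gain is already in the plan.

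**The case against.** The strongest reply is that nothing here is wrong. The covariates are pre-specified, and baseline TNS enters as a continuous variable with a by-visit term, which uses the stratification factor in finer form than the strata themselves. All of that stands.

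A reader might go further than the documents allow in four ways.

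- *That the primary estimate is biased, or its test invalid.* It is not. Omitting a baseline covariate from a linear model in a randomised trial does not bias the estimate on average, and the SE already includes chance imbalance in that covariate.
- *That precision is certainly lost, or a sizeable imbalance likely.* The loss depends on an effect the SAP does not quantify; at 0–1 point it is negligible. An imbalance of 10 points or more is a possibility of roughly one in four to one in three, not the expected outcome.
- *That the primary and subgroup models conflict.* A subgroup model with its own main effect always differs from the primary model. The same is true of gender, access type and vintage. Being named as a subgroup shows interest in effect modification, not prognostic strength.
- *That diabetes status will be complete.* Section 4.4 lists it but allows for missing baseline values.

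It is also fair to say that the plan partly covers the matter: diabetes will be tabulated by arm, and the interaction model yields effects within diabetics and non-diabetics. What it does not yield is a pre-specified overall estimate adjusted for diabetes, and that part of the concern remains.

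**Conclusion.** The point holds as a suggestion for improvement. The primary model is valid as written, and the stated power does not rely on diabetes. Leaving diabetes out forgoes some precision only if it predicts TNS change beyond baseline TNS.

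With 30–50% diabetic and a residual SD of 5–6, the forgone reduction in SE runs from nothing, through about 3–5% at 3 points of extra worsening, to about 8% at the most favourable corner (4 points, 50% diabetic, SD 5). Prevalence, residual SD and extra worsening are all assumptions.

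The case for acting is that the possible gain comes from a variable already listed for collection, the possible loss is close to nil, and the choice is fully credible only if made before unblinding. The weight is modest.

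**What to change.** Before unblinding, amend Section 5.1 to add baseline diabetes (yes/no, combining types 1 and 2) and diabetes-by-visit as fixed effects in the primary model. Carry the same terms into secondary outcomes 1a, 1c and 1e. Keep the current model, without diabetes, as a named sensitivity analysis.

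Because Section 4.4 allows missing baseline values, add a line on how missing diabetes status will be handled, so that no randomised participant drops out of the primary analysis on this account.

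The cost is a few sentences of SAP text and up to four fixed-effect parameters: one main effect and three for the interaction over four follow-up visits. No new data item is needed. If unblinding has already taken place, the adjusted model can still be reported, but as supportive and labelled post hoc.

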5.2. Secondary/SAEs outcomes

A summary of each secondary or safety endpoint will be provided. Continuous outcomes will be summarised by their mean (SD), while binary outcomes will be summarised by percentages.

Continuous: All continuous secondary endpoints without repeated measurements will be analysed using linear regression adjusted with its baseline counterpart. This applies to the exploratory analyses

Continuous repeated measurements: All secondary outcomes repeatedly measured over time (Secondary outcomes 1a, 1c, 1e) will be modelled using a Linear Mixed model including random intercept, randomisation and time categories as per the analysis of the main outcome (5.1). The Linear Mixed model will be formulated to use Direct Likelihood, which will allow for data that is missing at random.

Binary repeated measurement: will be analysed using generalised linear mixed model with a logit link and a binary distribution (logistic regression), for Secondary outcomes 1b and 1d.

Count: Count secondary endpoints, such as number of reported access-related AEs, will be modelled using a Poisson regression model, and a negative binomial model if there is overdispersion (>1.3). This will apply for secondary outcomes 2b, 2c, 2e, 2f, 2g, 2h.

Survival time: Survival curves and estimated median survival time will be generated according to the Kaplan-Meier method. Log-rank test will be used to assess the difference between the two survival curves by secondary endpoint. The hazard ratio between two treatments will be estimated with a Cox Proportional Hazards model if the PH assumption is met. This will apply for Secondary outcomes 2a and 2d.

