Composite Rank Score: A rank-based procedure combining mortality and functional neuropathy score will be used (Secondary outcome 4). Patients who die before the 48 month follow-up will be ranked from lowest (poorest outcome) to highest on their survival time (less survival time=lower rank). Then, those who are alive at the final follow-up with a TNS will be ranked from least to most favourable change in TNS from baseline (TNS follow-up – TNS baseline) . If participants are alive but do not have a valid TNS then they will be censored (Shortest Survival < Longest Survival < Lowest TNS change < Highest TNS change). Ranks between treatment groups will be compared with a log-rank test, and hazard ratio (with 95% confidence intervals) will be estimated with Cox proportional hazards regression. The main assumption underlying the composite ranking is that death at any time is worse than the greatest increase in TNS.

Sensitivity test for missing data in the main outcome: A sensitivity analysis of the missing at random assumption in the main outcome will be made with a delta-adjustment tipping point analysis. If a significant difference is found between the groups we will use a marginal delta adjustment method with a tipping point. We will impute missing visits (using a non-monotone MCMC method), then add a constant (delta) to the imputed data until the difference is no longer significant ($p>0.05$). If the value of delta required to overturn significant results is implausible then we will consider the results to be robust.

Further analyses: Further analyses for the cohort phase of the study will be subject to a separate report when data is available.

Serious adverse event outcomes:

Serious adverse event outcomes will be independently categorized by two authors into the following groups (as defined above):

- Access failure
- Septicaemia
- Cardiovascular event
- Surgery for carpal tunnel syndrome
- Parathyroidectomy surgery
- Fractures requiring or occurring during a hospital admission
- Other

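### The only infection outcome, septicaemia (2c), counts culture-positive episodes with no identified source, so an all-source count broken down by source should be reported beside it

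*SAP*

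**What the plan says.** Section 5.1 of the SAP lists eight safety outcomes, 2a to 2h. Three passages define where an infection could be counted:

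- Outcome 2c: "Episodes of septicaemia defined as blood culture positive septic episode without defined source".
- Outcome 2a: "Time to access failure, defined as thrombosis or fistula requiring revision". Outcome 2b uses the same definition: "Number of discrete episodes of access failure, defined as above".
- The other five are mortality, cardiovascular events, carpal tunnel surgery, parathyroidectomy and fractures.

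Section 5.2 (Secondary/SAEs outcomes) assigns 2c to Poisson regression, or negative binomial regression if there is overdispersion: "This will apply for secondary outcomes 2b, 2c, 2e, 2f, 2g, 2h". The same section sorts serious adverse events by the section 5.1 definitions: "Serious adverse event outcomes will be independently categorized by two authors into the following groups (as defined above". The groups that follow are access failure, septicaemia, cardiovascular event, the two surgical groups, fractures, and Other.

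Section 2.1 describes the trial as open-label. Section 5.1 says that the neuropathy assessors were blinded. The SAP does not say whether the two authors who categorise serious adverse events were.

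**The concern.** A reader told that septicaemia did or did not differ between haemodiafiltration and haemodialysis will take the statement to cover bloodstream infection in general. Outcome 2c covers only the part for which no source was identified. The rate of bacteraemia with an identified source could differ between arms without showing in 2c or in any other infection outcome.

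The definition also makes inclusion depend on a finding other than the infection itself. Two identical positive cultures are treated differently if one site identified a source and the other did not. Treatment is known to the clinicians who look for the source, and the classification is later made by two authors whose blinding is not stated. Systematically fuller source work-up in one arm would lower that arm's count with no difference in infection.

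**Working it through.** The SAP has no figure to reproduce here. The check is to follow each kind of culture-positive septic episode through the definitions.

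| Episode | Outcome 2c | Serious adverse event group |
|---|---|---|
| No source identified | Counted | Septicaemia |
| Source outside the access (chest, urine, wound) | Not counted | Other, unless another listed definition is met |
| Source is the access, without thrombosis or fistula revision | Not counted if the access is a defined source; counted if it is not | Other, or septicaemia, accordingly |
| Source is the access, with thrombosis or fistula revision | As the row above | Can be access failure, and so enter 2a and 2b |

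Three observations follow.

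1. The second row is lost from 2c on any reading. The third and fourth rows depend on a term that the SAP leaves undefined.
2. In the fourth row the episode is counted as an access event, but if the access is a defined source it is still missing from the septicaemia count.
3. Other is not a numbered outcome, so none of the models in section 5.2 is assigned to it. The count paragraph there mentions access-related adverse events as an example, but the only access count that section 5.1 defines is 2b.

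**How source-finding enters the rate ratio.** Let λ be the true rate of all culture-positive septic episodes in an arm, and s the share with a defined source. Outcome 2c then estimates λ(1 − s), and its rate ratio is

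(λ₁/λ₀) × (1 − s₁)/(1 − s₀).

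The SAP gives neither λ nor s, so the following values are assumptions that show the mechanism only.

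- If s is 30%, 50% or 70% in both arms, 2c retains 70%, 50% or 30% of all episodes. The second factor is 1, so the ratio is not distorted.
- With equal true rates and a source found in 60% of episodes in one arm and 40% in the other, the ratio is 0.40/0.60 = 0.67. With the arms exchanged it is 0.60/0.40 = 1.50.
- With equal true rates and 50% in each arm, the ratio is 0.50/0.50 = 1.00.

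**The case against.** The narrow definition may be deliberate. When two dialysis modalities are compared, unexplained bacteraemia is a sensible way to look for infection from the dialysis or substitution fluid. An all-source count adds chest, urinary and wound infections, which could dilute an effect of modality. The wording may also come from the protocol, which is not at hand. The SAP is dated January 2019, describes data collection in the past tense and already reports baseline results, so redefining a safety outcome at that stage would be hard to defend. These arguments stand. They are reasons to keep 2c and to supplement it rather than replace it.

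Several stronger readings are tempting and are not supported:

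- *All access infections drop out of 2c.* The SAP never says that the access is a defined source. The condition could be meant to exclude only episodes explained by a focus unrelated to dialysis.
- *They all end up in Other.* This is inferred from the list of groups, and it fails for episodes with thrombosis or fistula revision.
- *Baseline access gives the size.* Section 5.2 says that "the clear majority of participants (78%) were using an AVF at baseline", so 100% − 78% = 22% used something else. That is a share of participants. It says nothing about septic episodes or their sources, and fistula users can have access infections too.
- *Differential source-finding has biased the comparison.* Section 4.1 recruited from centres able to offer both modalities, so both arms were treated in units of the same kind. A 20-point difference between arms in source-finding is hypothetical.
- *A stated amount of precision is lost.* A smaller count does give a wider interval, but the unsourced and all-source counts are different outcomes, and nothing in the SAP fixes the ratio between them.

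**Conclusion.** The point holds as a limit on what the trial can conclude about infection safety. Outcome 2c is the only infection outcome, and on its plain wording it leaves out every culture-positive septic episode with an identified source. Whether access-related episodes are among those left out turns on a term that the SAP does not define. Inclusion further depends on whether a source was found, under open-label care.

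The size cannot be stated. The SAP supports no estimate of the number of episodes omitted, and it does not show that the 2c rate ratio is biased. The conclusion rests on two assumptions: that the wording is applied literally, and that nothing in the unseen protocol widens it. The primary neuropathy analysis and the mortality analysis are unaffected. This is an inexpensive improvement to one secondary safety outcome.

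**What to change.** Keep outcome 2c as defined, and make these additions to sections 5.1 and 5.2 of the SAP:

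1. State whether the dialysis access counts as a defined source.
2. Add a supplementary count of all blood-culture-positive septic episodes whatever the source, analysed with the Poisson or negative binomial model already planned for 2c.
3. Report that count by arm in three groups: access-related, other identified source, and no identified source.
4. Have the two authors who categorise serious adverse events assign the source blinded to allocation where feasible, and record whether this was done.

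The cost is SAP wording and one extra coding field in a categorisation that is already planned. There are two downsides. The breakdown relies on the source information recorded in the event reports, and some episodes may prove unclassifiable. The all-source total will also include episodes unrelated to dialysis, which the three groups keep apart.
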